15.3 Statistical Hypotheses

Primary Outcomes:

1. Both low- and high-dose topiramate will be more efficacious than placebo at reducing the percentage of heavy drinking days (PHDD) and increasing the continuous abstinence rate for smoking determined by a combination of self-report and CO monitoring after the TQD, and in the last 4 weeks of treatment.
2. High-dose topiramate will be more efficacious than low-dose topiramate at reducing PHDD and increasing the continuous abstinence rate for smoking determined by a combination of self-report and CO monitoring after the TQD, and in the last 4 weeks of treatment.

Secondary Outcomes:

3. Both low- and high-dose topiramate will be more efficacious than placebo at improving quality of life and reducing craving, after the TQD, and in the last 4 weeks of treatment.
4. High-dose topiramate will be more efficacious than low-dose topiramate at improving quality of life and reducing craving, nicotine and alcohol withdrawal symptoms and negative affect after the TQD, and in the last 4 weeks of treatment.
5. **Exploratory Outcomes:** Both low- and high-dose topiramate will be more efficacious than placebo at improving nicotine and alcohol withdrawal symptoms and negative affect in the last 4 weeks of treatment after the TQD.
6. Improvements in quality of life and craving reductions will be predictably associated with reduced PHDD, increased continuous abstinence rates for smoking, or both, irrespective of treatment group.

15.4 Subject Populations

The ITT population will be used for the primary analysis and is defined as the subjects who are randomized into the study. The evaluable population is defined as those subjects randomized to the study who completed at least 6 consecutive weeks of maintenance investigational product administration with a dose of at least 50 mg per day for at least 5 days of each 7-day weekly period. The safety population includes all subjects who received at least one dose of investigational product.

Analysis: Data will be summarized with respect to the primary and secondary outcome measures, demographics, and baseline characteristics. In general, quantitative variables will be summarized with standard descriptive statistics (e.g., range, quartiles, means, standard deviations), while frequency tables will summarize categorical variables. Group comparison for quantitative variables will be performed using standard two-sample t-tests or analysis of variance as appropriate. Highly skewed variables may be transformed prior to inferential comparison, or non-parametric methods may be used if needed. Group comparison for categorical variables will be analyzed with two-sample comparisons of proportions, or chi-square tests as appropriate.

The primary efficacy variables will be the PHDD for the drinking outcome and the continuous abstinence rate for the smoking outcome (during the last 4 weeks of treatment, i.e., weeks 15–18 inclusive), respectively. The secondary efficacy variables will be quality of life and measures of alcohol and nicotine craving.

Exploratory outcome variables will include other: 1) measures of drinking severity (i.e., DDD) and abstinence (i.e., percentage of days abstinent; PDA) averaged across either the entire double-blind period or the last 4 weeks of treatment, and 2) smoking measures including the point prevalence abstinence rate and the CO level over either the entire double-blind period or the last 4 weeks of treatment; 3) psychological assessments including measures of nicotine and alcohol withdrawal (WSWS, MOS-Sleep, CIWA-Ar), negative affect (PANAS, CES-D), dependence (FTND), drinking behavior (DrInC) and compliance (BBCET).

The general approach to statistical analyses will be the same as what we utilized in our previous studies.[4, 5] All randomized subjects will be included in the analysis using the intent-to-treat principle. Statistical analyses will be conducted using SAS 9.1 (SAS Institute Inc., Cary, NC).[6]

Primary Outcomes Analytical Models:

We will use generalized linear models (GLM) to estimate treatment effects on PHDD and logistic regression for abstinence. We will adjust for baseline covariates on the same drinking or smoking variables. For the drinking and smoking variables, that baseline is the averaged value for the 90-day period prior to the screening visit. Other potential covariates shall include age, gender, and ethnicity. We also will consider the treatment period up to the TQD as an additional set of covariates for analyses that focus on the last 4 weeks of treatment. The residuals from our analyses will be checked for normality by computing their skewness and kurtosis and will be checked for homogeneity of variance by plotting them in a histogram and against predicted outcomes. Standard transformations will be employed to improve the distributions when required (i.e., square root or log transformation).

If, however, there is a differential attrition rate (i.e., if dropout is informative), we shall consider other approaches to handle repeated-measures data that can be adopted to obtain valid results.[7, 8]

Exploratory Analytical Models:

We also will use the more advanced two-part random-effects model[9, 10] to analyze the daily drinking and smoking record. Such a model can simultaneously characterize the frequency (odds of daily drinking or smoking being zero) and quantity (number of drinks on a drinking day or number of cigarettes smoked on a smoking day) of drinking and smoking outcomes, respectively. It is more efficient and can tackle non-normality in the drinking or smoking level. We also are interested in trajectory analysis of different treatments over time to capture differences in these outcomes. Such analysis is more clinically intuitive and could be more powerful than the analysis based on endpoint.

The Kaplan-Meier survival method will be used to compare time to achieve continuous abstinence between the treatment groups. Homogeneity between different arms will be tested with the log-rank test. Additionally, we will use the Cox proportional-hazards model to estimate the relative likelihood (i.e., magnitude of the treatment response) between the treatment groups for achieving continuous periods of abstinence. For the Cox regression model, potential confounding variables such as age of onset for alcoholism (less than 26 years old or 26 years and

older), gender, weight, and baseline smoking level will be considered as potential covariates for inclusion in the final analytic model.

If the saliva cotinine level satisfactorily achieves criteria for normality as longitudinal data, we will compare the groups using a mixed-effects linear model, accounting for a three-group design as well as the repeated measure of weeks (when appropriate). Otherwise, salivary cotinine level will be dichotomized as negative if ≤ 15 ng/ml and positive if > 15 ng/ml and analyzed using the generalized linear mixed models.

Logistic regression analysis will be used to compare point prevalence abstinence rates for the topiramate vs. placebo groups. We will determine point prevalence abstinence rates by a report of not smoking (0 cigarettes/day) for the entire period prior to a particular visit and an expiratory CO of < 10 ppm at the present visit.

[figure not shown]

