A physical exam will be performed including the subject's weight. Vital signs will be taken, an ECG will be performed, and the subject will be queried on medication use in the 90 day period prior to signing consent. Subjects will be instructed that no new prescription/non-prescription medications are to be taken between the start of screening and randomization without informing the study staff. The subject's demographics will also be collected at this visit.

A urine drug test will be performed using a point of care test strip. Blood will be collected for hematology, chemistry and optional genotyping assessments. Urine will also be collected for urinalysis. Saliva will also be collected for cotinine level.

The MINI will be performed to assess diagnoses of psychiatric disorders in accordance with DSM-4 criteria. At screening the following questionnaires will be administered: Fagerström Test for Nicotine Dependence, AUDIT, CIWA-AR, Q-LES-Q, The Alcohol Craving Visual Analog Scales, The Nicotine Craving Visual Analog Scales, Wisconsin Smoking Withdrawal Scale, PANAS, CES-D, MOS-Sleep, Baseline Drug Use, and DrInC. Screening may be completed in a single visit or over two visits (e.g., a hematology or chemistry test needs to be repeated).

Subjects will be required to provide the name, phone number, and address of up to three contact persons who are likely to know their whereabouts.

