13.4 Intervention Phase

Subjects will be seen in person at the clinical site for 17 visits (screening, intervention phase and the one month follow-up visit) and will complete the three month follow-up visit over the phone. All subject clinic visits will be collected on source documents and entered into an electronic database, or entered directly into an electronic database and printed out and placed in the source documentation binder. Clinic visits should be scheduled on the same day of the week that the subject was randomized, if possible, but a 3-day window is allowed. In the event of a missed visit, subjects will have until the end of the same week to reschedule an appointment or if the subject is unable to visit the clinic then the visit may be conducted over the telephone.

If the subject comes to a visit outside the allowed window, assessments scheduled for this visit will be conducted and data will be recorded as if it were for that week's scheduled visit and recorded as an unscheduled visit. At each of the clinic visits during the intervention phase, subjects will receive a brief session with one or more study staff members who will systematically assess AEs since the last visit, take vital signs, measure weight, conduct a BBCET session, administer questionnaires, ask about concomitant medication use and contraceptive method, and assess drinking and smoking using the TLFB. A new supply of investigational product will be given and the medication bottle(s) from the previous period will be collected. Blood will be collected for chemistries and hematology and a physical exam and electrocardiogram will be performed at Week 19 (visit 15). Women of child bearing potential will have a repeat pregnancy test during Weeks 1, 4, 7, 10, 16 and 19. An alcohol breathalyzer will be administered at each visit to determine if the subject has a BAC ≤ 0.020 to complete the visit. A urine drug test will be performed intermittently throughout the study. If the subject misses a visit in which safety measures were collected, the safety measures should be collected at the next in-clinic visit.

The following assessments will be administered at each study visit during the intervention phase (Week 1, 2, 3, 4, 5, 6, 7, 8, 9, 10, 12, 14, 16, 18 and 19): Q-LES-Q, Alcohol Craving Visual

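### No model is specified for the secondary outcomes (quality of life, alcohol and nicotine craving), so a general t-test/ANOVA rule applies by default and leaves baseline and repeated-visit data out of the stated analysis

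*Combined protocol and SAP*

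**What the plan says.** Section 15.4 states that "The secondary efficacy variables will be quality of life and measures of alcohol and nicotine craving". Section 15.3 attaches hypotheses 3 and 4 to them. Hypothesis 3 begins "Both low- and high-dose topiramate will be more efficacious than placebo at improving quality of life and reducing craving, after the TQD, and in the" and ends with the last four weeks of treatment, so there are two time windows.

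The general analysis paragraph of Section 15.4 opens "Data will be summarized with respect to the primary and secondary outcome measures, demographics, and baseline characteristics" and then gives the rule "Group comparison for quantitative variables will be performed using standard two-sample t-tests or analysis of variance as appropriate", allowing transformation or non-parametric methods for skewed variables. The model text that follows has two headings only, one for primary and one for exploratory models. Under the primary heading: "We will use generalized linear models (GLM) to estimate treatment effects on PHDD and logistic regression for abstinence", and "We will adjust for baseline covariates on the same drinking or smoking variables". Under the exploratory heading, the two-part random-effects model is for the daily drinking and smoking record, and the mixed-effects linear model is for saliva cotinine.

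The Q-LES-Q and both craving scales are listed at screening (Section 13.2: "AUDIT, CIWA-AR, Q-LES-Q, The Alcohol Craving Visual Analog Scales, The Nicotine Craving Visual Analog Scales"). They are listed again for the treatment phase (Section 13.4: "The following assessments will be administered at each study visit during the intervention phase"), at weeks 1 to 10, 12, 14, 16, 18 and 19. Section 3, Table 1 agrees. Section 12.1 has the first capsule taken on the evening of Day 1, so the visit 1 value is pre-dose.

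**The concern.** The secondary scales have two pre-dose values and 14 later intervention-phase values per subject, yet the only stated method that reaches them is one that, as written, uses neither a baseline nor more than one time point. No sentence says which visit or average is compared for either window.

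The plan's own reasoning points the other way. Its exploratory text says that analysing trajectories may be more powerful than analysing an endpoint. It also gives a mixed model to saliva cotinine, which Section 14.26 collects only before randomization and at visit 15. Scales measured at 16 occasions have no such model.

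At stake is how precisely hypotheses 3 and 4 are tested, and how many randomized subjects can contribute to the last-four-weeks comparison.

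**Working it through.** **1. The plan's own figure.** The documents give no power figure for the secondary outcomes. The 98 per arm used below comes from Section 15.5: 10% vs 28%, alpha 0.017, power 0.80. Two-sided with pooled variance (sidedness is assumed; it is not stated):

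n = [z(α/2)·√(2·0.19·0.81) + z(β)·√(0.10·0.90 + 0.28·0.72)]² / 0.18²
= [2.387·0.555 + 0.842·0.540]² / 0.0324 ≈ 98.

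The figure reproduces (99 at exactly 0.05/3). The Section 4 dropout figure also reproduces: 294 × 0.70 = 205.8, stated as 206, or 68.6, about 69, per arm.

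**2. Visit count.** The intervention phase has 15 visits (Section 13.4). Visit 1 is pre-dose, which leaves 14 (weeks 2–10, 12, 14, 16, 18, 19). Weeks 16 and 18 are the only scheduled visits inside weeks 15–18. The week 19 visit falls after the last dosing day, Day 126 of week 18 (Section 12.1).

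**3. Assumptions.** The documents give no SD, effect size or correlation for these scales. Assumed: baseline–outcome correlation r of 0.3 to 0.7, a true difference of 0.4 SD, and two-sided alpha 0.05/3 = 0.0167. Section 15.5 states that alpha only for the smoking and drinking power calculations; its use here is also an assumption.

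**4. Baseline adjustment alone.** The variance factor is 1 − r². The difference detectable with 80% power is (2.394 + 0.842)·√(2(1 − r²)/n). Power for 0.4 SD is Φ(0.4/√(2(1 − r²)/n) − 2.394).

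| Analysis | Variance factor | Detectable SD, n = 98 | Power, n = 98 | Power, n = 69 |
|---|---|---|---|---|
| No adjustment | 1.00 | 0.46 | 0.66 | 0.48 |
| r = 0.3 | 0.91 | 0.44 | 0.71 | 0.53 |
| r = 0.5 | 0.75 | 0.40 | 0.80 | 0.63 |
| r = 0.7 | 0.51 | 0.33 | 0.94 | 0.82 |

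For r = 0.5 and n = 98: √(2·0.75/98) = 0.1237; 0.4/0.1237 = 3.233; 3.233 − 2.394 = 0.839; Φ = 0.80. In sample-size terms, 98/0.75 ≈ 131 per arm would be needed without adjustment to match 98 with it.

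The n = 98 column assumes that every randomized subject has a value in the window. The n = 69 column assumes that only completers do. Section 12.2 lets subjects who stop medication stay in the study, so the real number may lie between them.

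**5. Using the repeated visits as well.** Under compound symmetry with correlation ρ, the variance of a mean of k visits adjusted for the mean of m baselines is (1 + (k − 1)ρ)/k − mρ²/(1 + (m − 1)ρ), relative to a one-visit unadjusted test. With k = 2 (weeks 16 and 18) and m = 2 (screening and visit 1), this is 0.51, 0.42 or 0.27 at ρ = 0.3, 0.5 or 0.7. Part of that comes from averaging two visits, which a t-test on the mean would share: at ρ = 0.5, 0.75 of the one-visit variance without baselines against 0.42 with them. These figures lean on a simple correlation structure and are less secure than step 4.

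**The case against.** The strongest case against is that the plan never assigns t-tests to these scales. The rule is introduced as a general approach and qualified by its closing words. The same paragraph also covers the primary outcomes, which then receive their own models. Section 15.4 further says that the general approach follows the earlier trials, and Section 15.5 shows that weekly heavy drinking in the earlier multi-site trial was handled with a mixed model. This stands in part. The secondary outcomes fall under the rule by default, not by name. But the pointer states no model for quality of life or craving, and Section 15.5 concerns heavy drinking only. The repeated-measures fallback in Section 15.4 sits under the primary models, depends on differential attrition and commits only to considering alternatives.

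A reader might infer that the plan commits to an unadjusted, completers-only analysis that discards every other measurement. The documents do not support that. No sentence excludes a covariate or a change score, and Section 15.4 says that all randomized subjects will be included under intention-to-treat. What is missing is any method that would deliver that inclusion for these scales. The early-termination visit (Section 13.6) collects the visit 15 assessments, but its date need not fall in weeks 15–18.

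It is also fair to say that an unadjusted comparison of randomized arms is not biased in itself.

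**Conclusion.** The point holds as a gap in specification with an efficiency cost. Section 15.4 names no model for the secondary outcomes, and the default rule carries neither baseline adjustment nor repeated measures. Baseline adjustment alone would cut variance by 9% to 49% for r between 0.3 and 0.7. For an assumed 0.4 SD effect at r = 0.5, power goes from 0.66 to 0.80 at 98 per arm, or from about 0.48 to 0.63 at about 69. The correlation, effect size and alpha are all assumed, so these figures show the order of the gain and are not a forecast.

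Dropout adds a second consideration. A test on weeks 15–18 cannot use a subject with no value there. A likelihood-based model uses that subject's earlier visits and is valid under missing at random, a weaker assumption than a complete-case test needs. The primary outcomes are not affected. The change should be made, but the trial's main conclusions do not depend on it.

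**What to change.** For the Q-LES-Q and both craving scales, replace the general rule with a likelihood-based mixed model for repeated measures, using all post-baseline treatment visits. Include:
- arm, visit and arm by visit;
- baseline, as the mean of screening and visit 1;
- the randomisation factors in Sections 9 and 13.3 (age of onset, gender, drinks per drinking day, cigarettes per day).

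Take the three pairwise arm contrasts for both windows in hypotheses 3 and 4: the average of the post-TQD treatment visits, and the average of weeks 16 and 18. State whether the week 6 visit (the TQD itself) and the week 19 visit (after the last dosing day) count towards the first. Name the score analysed: Section 14.20 gives eight Q-LES-Q summary scales, three scored only when applicable, and each craving measure has four items, one worded in the opposite direction.

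For the repeated exploratory scales, use a baseline-adjusted repeated-measures model with contrasts at the visits where each is scheduled. The week 16 and 18 contrast cannot simply be copied. Section 13.4 lists the PANAS at weeks 1, 3, 5, 7, 9 and 19, the DrInC at weeks 1, 4, 6, 9, 12 and 19, and the MOS-Sleep at week 16 but not week 18.

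The cost is SAP wording and programming, fixed before unblinding. No new data are needed.

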9 STUDY DESIGN

Two hundred and ninety-four comorbid nicotine-dependent subjects with mild to severe alcohol use disorder who meet eligibility criteria will be randomized to 1 of 3 treatment groups — placebo, low-dose topiramate (up to 125 mg/day), or high-dose topiramate (up to 250 mg/day). Randomization will be achieved using a block randomization procedure in which treatment groups will be stratified to achieve a balance on age of onset for alcoholism (less than 26 years old or 26 years and older), gender, and drinks per drinking day (DDD) (<8 DDD or ≥ 8 DDD) and the number of cigarettes smoked (<20 or ≥ 20 cigarettes/day).

Following randomization, subjects will participate in an 18-week, double-blind treatment period during which they also will receive weekly BBCET, and a self-help manual for smoking cessation. Topiramate and matching placebo will be titrated for the first 5 weeks of the 18-week treatment period. The TQD will be at the beginning of the 6th week of treatment. Subjects will be instructed not to attempt smoking or alcohol cessation prior to the TQD. Setting a TQD at the end of medication titration enables stability of effects, comfort with the medication prior to attempting to cease alcohol and smoking consumption, and an appreciable buildup of medication. However, in cases where individuals either quit smoking or alcohol consumption prior to the TQD, counseling will be directed at helping them maintain their abstinence and reengaging their efforts in the event of relapse. If an individual finds that he or she cannot quit

smoking and/or consuming alcohol completely following the TQD, he or she shall remain in the study and counseling will be directed at the continued setting of reduction goals, with cessation as the ultimate target.

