13.3 Subject Randomization

Prior to randomization, data essential for eligibility will be reassessed. Drinking and smoking requirements during the time period between the screening visit and visit 1 will be reassessed. All essential data for assignment to a treatment group will be collected by the study staff on the randomization form.

Assignment to a stratum during randomization will be based on the following: age of onset (≤ 25 or >25), drinks per drinking day (DDD) during the 90 days prior to screening (<8 or ≥ 8), average number of cigarettes smoked per day during the 90 days prior to screening, and gender. Calculations will be made using the formulas below.

$$\frac{\text{90 Day SDU Total}}{\text{\# Drinking Days}} = \text{Drinks per Drinking Day (DDD)}$$

$$\frac{\text{90 Day Cigarette Total}}{\text{90 Days}} = \text{Average \# Cigarettes per Day}$$

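### The primary models do not commit to the randomisation strata and allow post-randomisation, pre-TQD covariates: fix one main-effects set before unblinding (low to moderate priority)

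*Combined protocol and SAP*

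**What the plan says.** Section 9 says that "treatment groups will be stratified to achieve a balance on age of onset for alcoholism" (under 26, or 26 and older), gender, DDD (below 8, or 8 and above) and cigarettes per day (below 20, or 20 and above). The Abstract repeats this. Section 13.3 names the same four factors ("Assignment to a stratum during randomization will be based on the following: age of onset", and so on) and computes DDD and cigarettes per day over the 90 days before screening.

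The primary models are in section 15.4 under Primary Outcomes Analytical Models: a generalized linear model for PHDD and logistic regression for abstinence. One adjustment is firm: "We will adjust for baseline covariates on the same drinking or smoking variables", where "that baseline is the averaged value for the 90-day period prior to the screening visit". Two further sentences are open: "Other potential covariates shall include age, gender, and ethnicity", and, for analyses of the last 4 weeks, "We also will consider the treatment period up to the TQD as an additional set of covariates". The last 4 weeks (weeks 15–18) are the primary window. Section 9 states that "Topiramate and matching placebo will be titrated for the first 5 weeks of the 18-week treatment period", with the TQD at the start of week 6.

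Age of onset appears in the analysis text only as a possible covariate in the exploratory Cox model. Section 15.4 also says "The general approach to statistical analyses will be the same as what we utilized in our previous studies". The reports of those studies are not part of the documents, so any covariate rule in them cannot be checked.

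**The concern.** Three things follow from this text.

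1. **Estimand.** Pre-TQD consumption is recorded after up to five weeks of assigned drug, so it may already carry part of the treatment effect. Conditioning on it moves the estimate away from the total effect at weeks 15–18. The plan leaves open whether this will be done.
2. **Strata.** The allocation is balanced on four factors, but two of them, age of onset and gender, have no committed term in either model. Baseline smoking probably covers cigarettes per day in the smoking model. Baseline PHDD is related to DDD but is not the same variable.
3. **Open choice.** No selection rule or decision date is given. Section 15.5 sets each pairwise test at 0.05/3, and a covariate choice made after unblinding could erode that level.

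**Working it through.** **The plan's own figure.** Section 15.5 takes 10% against 28%, alpha 0.017 per pair and power 0.80, and obtains 98 per arm. With pooled variance, two-sided:

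n = [2.387·√(2·0.19·0.81) + 0.842·√(0.10·0.90 + 0.28·0.72)]² / 0.18² = (1.324 + 0.454)² / 0.0324 ≈ 97.7, so 98.

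The figure reproduces (99 at exactly 0.05/3). Nothing below changes it.

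**Number of models.** Age, gender and ethnicity in or out, and the pre-TQD set in or out: 2³ × 2 = 16 per endpoint.

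The documents give no prognostic strengths, so every strength below is an assumption.

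**Pre-TQD adjustment, PHDD.** Assume the effect grows linearly from week 1. Its mean over weeks 1–5 is 3 units and over weeks 15–18 is 16.5 units, so the early share is 3/16.5 = 18.2%. With equal variances, the within-arm coefficient equals the partial correlation r. Adjustment removes 0.182·r of the effect and multiplies the standard error by √(1−r²). Signal-to-noise changes by the ratio (1−0.182r)/√(1−r²). Power is Φ(ratio × (2.394 + 0.842) − 2.394).

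| r | Effect removed | SE reduction | Ratio | Power (from 0.80) |
|---|---|---|---|---|
| 0.3 | 5% | 4.6% | 0.99 | 0.79 |
| 0.5 | 9% | 13.4% | 1.05 | 0.84 |
| 0.7 | 13% | 28.6% | 1.22 | 0.94 |

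The result depends on how much of the effect runs through the early weeks. In a simulation with a total effect of 0.40 and unadjusted power of about 0.83, adjusted power was 0.95, 0.69 and 0.31 when 0%, 25% and 50% of the effect ran through pre-TQD consumption. The adjusted estimates were 0.40, 0.30 and 0.20.

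**Omitted strata, PHDD.** If the strata explain a share R² of residual variance, the true level of the unadjusted test is 2·[1−Φ(2.394/√(1−R²))]. For R² = 1%, 5% and 10% this gives 0.0161, 0.0140 and 0.0116.

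**Omitted strata, smoking.** Simulation of low dose against placebo: 294 subjects, 16 strata, blocks of 6 (assumed), complete outcomes (assumed), abstinence 10%/28%/28%, Wald test at 0.0167, 20,000 runs per setting. Power moves as follows when age of onset, gender and DDD are added to arm and cigarettes per day. Age of onset and gender carry the stated odds ratio, DDD its square root per SD.

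| Odds ratio | Without | With | Gain (points) |
|---|---|---|---|
| 1.0 (control) | 0.8089 | 0.8111 | 0.2 |
| 1.25 | 0.8065 | 0.8105 | 0.4 |
| 1.5 | 0.8083 | 0.8184 | 1.0 |
| 2.0 | 0.8122 | 0.8321 | 2.0 |

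The 0.2 at odds ratio 1.0 is a small-sample artefact. Net of it, the gain is about 0.2, 0.8 and 1.8 points.

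**Open choice, PHDD.** Linear model, 98 per arm, no effect, baseline PHDD always in. Age, gender and ethnicity each explain 1% or 3% of residual variance, and pre-TQD PHDD has partial correlation 0.3 to 0.7. Taking the smallest p-value at nominal 0.0167, over 20,000 runs per setting:

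- fixed set: 0.016–0.019
- smallest of 8 sets (age, gender, ethnicity): 0.020–0.026
- smallest of 16 sets: 0.027–0.047

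Repeat simulations of the 16-set case, with somewhat different strengths, lay between 0.021 and 0.045. The low end is the case where the optional covariates have no prognostic value.

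**Open choice, smoking.** Logistic model, 10% in both arms, 3,000 runs, Monte Carlo SE about 0.002: fixed set 0.010–0.011, smallest of 8 sets 0.013, smallest of 16 sets 0.018. The last figure is within simulation error of 0.0167, and a repeat run stayed below 0.0167. The Wald test is conservative at this event rate.

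**The case against.** **The wording can be read as a commitment.** The verb form in the age, gender and ethnicity sentence could mean that all three go in. The sentence still calls them possible covariates, and the pre-TQD sentence only promises to consider. On either reading age of onset is absent and the pre-TQD terms are undecided.

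**Nothing suggests selection by p-value.** This stands. A reader might infer that the open list inflates the trial's false-positive rate. The documents do not support that: the PHDD figure is a worst case under assumed strengths, and no clear inflation appeared for smoking, the endpoint that sets the sample size.

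**Pre-TQD adjustment may help.** This also stands. A reader might infer that it costs power, but under the linear build-up power is flat or higher. The objection to it concerns what is estimated. The instruction not to attempt cessation before the TQD reduces early change but does not exclude it, since section 9 itself plans for people who quit early.

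**The strata gain is small.** Agreed. It would not justify a change on its own.

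**Other choices stay open.** Section 15.4 also leaves open transformations, non-parametric alternatives and the response to differential attrition. Fixing the covariates does not settle those.

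**Conclusion.** The point holds in a limited form, at low to moderate priority. The firmest part is that outcome data collected after randomisation, during titration, may enter the primary weeks 15–18 models. Including them would change the estimand and, if the effect builds linearly, remove about 5–13% of the PHDD effect. Net power would then be 0.79/0.84/0.94 against 0.80, and it would fall appreciably only if more of the effect ran through the early weeks.

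The mismatch with the strata is real but inexpensive. A reader might infer bias or an inadequate sample size from it; neither follows. The PHDD test runs at about 0.016 to 0.012 instead of 0.0167 if the strata explain 1–10% of residual variance, and smoking power loses about 0.2–1.8 points. The open choice matters for PHDD only, with a per-pair error of about 0.03–0.05 at worst under the assumed strengths and only if the smallest p-value were taken.

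**What to change.** Before unblinding, replace the two open covariate sentences in section 15.4 with one dated, fixed main-effects set per model:

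- **PHDD model:** arm, baseline PHDD, age-of-onset group (<26/≥26), gender, continuous baseline DDD, continuous baseline cigarettes per day.
- **Smoking model:** arm, continuous baseline cigarettes per day, age-of-onset group, gender, continuous baseline DDD. State that the odds ratio is conditional on these covariates.

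Do not fit a 16-cell stratum term: 294/16 is about 18 subjects per cell, or about 6 per arm. Move age, ethnicity and the pre-TQD terms to labelled sensitivity or exploratory analyses.

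**Cost.** All variables are already collected before randomisation, so there is no added patient burden and no change in sample size. Because the analysis plan is part of the protocol, the change needs IRB approval before it is implemented (section 13.10, PI responsibilities). The statistical downside is few abstainers per parameter in the logistic model, which has 6 non-intercept parameters. With 10% abstinence in all arms there are 294 × 0.10 = 29.4 abstainers, or about 4.9 each. With 10%/28%/28% there are 98 × 0.66 = 64.7, or about 10.8 each. In the sparse case simulated type I error for one pair was 0.010–0.011 with the added terms, below 0.0167.
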